## 6.4.3. Baseline Definition, Change from Baseline

According to Table 5 of the CSP ("Schedule of Assessments and Procedures"), the second visit (V2) is defined as "Baseline". However, the definition of the "Baseline" which is used to

CONFIDENTIAL Page 32 of 139

derive any changes of assessments during study conduct, e.g., laboratory parameters, depends on the timing of the first IP administration and can therefore be different from Baseline/Day 1/Visit 2. Therefore, unless otherwise stated, for the purpose of analysis baseline value is the last non-missing value prior to or at the date of the first dose of IP, considering also unscheduled visits. For participants who do not receive IP during the study, baseline is defined as the latest, non-missing collected value on or before Study Day 1.

Change from baseline will only be calculated for measures that have post-baseline records. Change from baseline is calculated as:

visit value – baseline value.

If either the baseline or visit value is missing, the change from baseline will be set to missing as well.

For summaries, whenever baseline is presented, the above baseline definition is used. That is, the baseline summary presented is in general not the summary of the (CSP defined) Baseline/Day 1 visit. Screening values will be listed but not summarized. Throughout the document, Baseline (capital B) refers to the visit Baseline/Day 1; baseline (lower case b) refers to the values derived using the baseline definition above.

### 6.4.4. Multiple Assessments

If a participant has more than one numeric record for a specific parameter of interest at a specific visit and/or timepoint for any reason (but the same source, e.g., central lab), the latest of that specific data at that visit and/or timepoint will be considered in summary tables, unless otherwise stated.

If a result will be assessed by local and central laboratories, central assessment will be used for reporting purposes.

Data from all assessments (local and central; scheduled and unscheduled), including multiple assessments, will be included in listings.

#### 6.4.5. Calculation of Study Day

In general, the date of randomization and the date of first IP administration should coincide, both expected to occur at Visit 2, Baseline. However, discrepancies between these dates may arise which leads to two reference dates to be defined in this study:

- On-Study Estimands: the reference date is the date of randomization and will be used to calculate Study Day for efficacy measures, e.g., time to event.
- On-IP and On-Treatment Estimands: the reference date is the very first date of IP administration and will be used to calculate Study Day for safety measures, e.g., to assess whether an AE is treatment-emergent or not, additional sensitivity and supplementary analysis.

#### **Study Day for On-Study Estimands**

If the date of interest occurs on or after the date of randomization, then (efficacy) Study Day will be calculated as

 $(date\ of\ interest-date\ of\ randomization)+1.$ 

CONFIDENTIAL Page 33 of 139

If the date of interest occurs prior to the date of randomization, then (efficacy) Study Day will be calculated as

 $(date\ of\ interest-date\ of\ randomization).$ 

There is no efficacy Study Day 0.

#### **Study Day for On-IP and On-Treatment Estimands**

If the date of interest occurs on or after the date of initial IP administration, then the (safety) Study Day will be calculated as

 $(date\ of\ interest-date\ of\ first\ IP\ administration)+1.$ 

If the date of interest occurs before the date of initial IP administration, then the (safety) Study Day will be calculated as

(date of interest – date of first IP administration).

There is no safety Study Day 0.

#### 6.4.6. Calculation of Pack-Years

Number of pack-years smoked will be calculated as:

$$pack\_years = (packs\ smoked\ per\ day) * (years\ of\ smoke).$$

The following list defines the transformation required to calculate a single pack for the various substances. Note, 20 cigarettes define a single pack.

- Pipe: 1 pipe a day equals to 2.5 cigarettes per day
- Cigar: 1 cigar a day equals to 4 cigarettes per day
- Cannabis / marijuana: 1 joint/pipe a day equals to 2.5 cigarettes per day

#### 6.4.7. Durations, Exposure Days, Follow-up Time, Compliance

#### Duration

A duration between one date (*date1*) and another later (or the same) date (*date2*) is calculated using the following formula and presented by one decimal place, if not stated otherwise:

- Duration (days) = date2 date1 + 1
- Duration (weeks) = duration (days) / 7
- Duration (months) = duration (days) / (365.25 / 12)
- Duration (years) = duration (days) / 365.25

The duration on study will be calculated as number of days between date of randomization and EOS visit:

```
duration \ on \ study \ (days) = date \ of \ EOS - date \ of \ randomization + 1.
```

The duration of individual IP exposure will be calculated as number of days between date of first intake of IP and the date of last intake of IP (see Section 6.4.1).

```
exposure\ duration\ (days) = date\ of\ last\ IP\ intake\ -\ date\ of\ first\ IP\ intake\ +\ 1.
```

The above calculation does not account for protocol-allowed dose interruptions.

CONFIDENTIAL Page 34 of 139

The duration of treatment will be evaluated as follows:

(actual) treatment duration (days) = actual treatment duration (days)- $number\ of\ missed\ IP\ due\ any\ reasons.$ 

## Participant's Follow-up Time or Observation Time

The individual follow-up time / observation time in years will be calculated using the following formula:

$$follow - up \ time \ (years) = \frac{date \ of \ EOS - date \ of \ first \ IP \ intake}{365.25}$$
.

For participants ongoing at time of primary analysis, e.g., adolescents, the date of cut-off will be used as date of EOS.

#### **Compliance**

Participants will be required to bring all their used and unused IP supplies to in-clinic study visits during the treatment period or, if the visit is being conducted virtually, have all used and unused study drug supplies available to be accounted for. Compliance will be calculated by considering the number of dispensed and returned pills in the eCRF as follows:

$$compliance (\%) = \frac{number \ of \ doses \ taken}{number \ of \ doses \ expected} * 100.$$

The number of doses expected is the number of doses a participant is "potentially" able to take. Missed doses for any reason, or any doses after treatment discontinuation will not be considered as "expected", hence excluded.

Missed IP or missed dose will be recorded in the participant's diary and eCRF. If participant's missed dose or days when dose was missed is unknown, the number of dispensed and returned pills in the eCRF will be evaluated to determine participants' number of doses missed. If the amount returned is missing in the eCRF, a worst-case approach will be used, and the returned number of tablets will be set to be equal to the dispensed number of tablets. This means that the participant took no dose from a particular dispensed kit.

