#### **10.4.4.** Major Protocol Deviations

The major protocol deviations will be identified based on a review of the study data prior to the database lock and unblinding. Major deviations may include the following:

- Violation of inclusion and/or exclusion criteria;
- Noncompliance with the dosing schedule (ie, subjects for whom compliance during the double-blind treatment period was not between 75% and 120%);
- Administration of prohibited concomitant medications that are expected to influence the measurement of the primary endpoints.

Major protocol deviations will be summarized and presented in data listings.

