## **10.4.5.** Treatment Exposure and Compliance

The cumulative exposure to study drug, including duration of treatment, total number of doses received, and cumulative amount of drug received (mg), will be summarized by treatment group.

Treatment compliance will be calculated as:

Compliance (%) at Visit X = (Number of doses taken up to the day preceding Visit <math>X / (Number of doses)

Number of expected doses up to the day preceding Visit X) \* 100

Treatment compliance will be listed by subject and summarized by treatment, based on the Safety Analysis Set.

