## 1. INTRODUCTION

The purpose of this Statistical Analysis Plan (SAP) is to describe the planned analyses to be included in the Clinical Study Report (CSR) for study INS1007-301.

The reader is encouraged to read the study protocol for details on the conduct of this study, the operational aspects of clinical assessments, and the timing for a participant to complete the participation in this study.

The SAP is intended to be aligned with the protocol. However, the SAP may contain more details or other types of analyses. Differences in descriptions or explanations provided in the study protocol and this SAP, are discussed in Section 13. The SAP is based upon the following documents:

- Clinical Study Protocol (CSP) (Global) Amendment 4, Version 7, dated 13 Feb 2024,
- Electronic Case Report Form (eCRF) Version 14, dated 21 Sep 2023.

Details pertaining to the scope of analyses for Data Monitoring Committee (DMC) review are provided in the DMC SAP.

The analyses described in this plan are considered a priori, in that they have been defined prior to database lock and unblinding. Any analyses not described herein performed subsequent to unblinding will be considered post hoc and exploratory.

CONFIDENTIAL Page 12 of 139

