### 9.1. Exposure to IP, Compliance, and IP Interruption

Exposure to IP will be descriptively summarized by treatment group including the below (see Section 6.4.7 for derivation of data points):

- Duration of treatment of IP,
- Duration of treatment with IP by categories:
  - o <4 weeks
  - o <12 weeks
  - $\circ$  >=12 weeks to <24 weeks
  - $\circ$  >=24 weeks to <36 weeks
  - $\circ$  >=36 weeks to <=52 weeks
  - $\circ$  >52 weeks,
- Cumulative duration of treatment with IP by categories:
  - $\circ$  >=12 weeks,
  - $\circ$  >=24 weeks,
  - $\circ$  >=36 weeks.
- Duration of IP exposure,
- Duration of IP exposure by categories:
  - o <4 weeks
  - o <12 weeks
  - $\circ$  >=12 weeks to <24 weeks
  - $\circ$  >=24 weeks to <36 weeks
  - $\circ$  >=36 weeks to <=52 weeks
  - $\circ$  >52 weeks,
- Cumulative duration of IP exposure by categories:
  - $\circ$  >=12 weeks,
  - $\circ$  >=24 weeks,
  - $\circ$  >=36 weeks.
- Number and percent of participants compliance to IP, categorized as:
  - >120%, >100-<=120%, >=75-<=100%, <75%,
- Number and percent of participants missed (at least one) IP intake,
- Basic summaries of number of days a participant missed IP intake,
- Number and percent of participants who missed IP due to COVID-19.

CONFIDENTIAL Page 73 of 139

<sup>6 The category "<4 weeks" will be a single category for duration of treatment of IP as well as for the duration of IP exposure.

A cross tabulation of IP randomized and IP received (actual received) will be generated by treatment group and dispensed visit, e.g., Day1, Week 4, Week 16, Week 28, and Week 40. The tabulation will count the number of participants as well the number of incorrect doses. The IP received category will separately count randomized but not treated participants.

In addition, the below listings will be produced:

- IP used from specific batches as provided by the interactive response system,
- randomization scheme and codes.

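### SAP 6.4.7 removes missed doses from the compliance denominator, so the SAP 9.1 compliance categories understate under-dosing, and Section 13 does not declare the departure from protocol 10.4.5

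*SAP*

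**What the plan says.** **SAP 6.4.7, Compliance.** Compliance is doses taken divided by doses expected, times 100, worked out from dispensed and returned pills. On the denominator: "Missed doses for any reason, or any doses after treatment discontinuation will not be considered as" expected, and so they are excluded. Missed doses are recorded in the diary and the eCRF. If they are unknown, they are derived from the same dispensed and returned counts. If the returned amount is missing, "a worst-case approach will be used, and the returned number of tablets will be set to be equal to the dispensed number of tablets", meaning that no dose was taken from that kit.

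**SAP 6.4.7, Duration.** The treatment-duration line reads "actual) treatment duration (days) = actual treatment duration (days"), from which the number of missed IP doses is then subtracted.

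**Protocol 10.4.5.** The divisor is "Number of expected doses up to the day preceding Visit X". No exclusion of missed doses is stated. Protocol 5.5 sets the noncompliance limits at below 75% and above 120%, and exempts only interruptions instructed by the Investigator for safety.

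**Outputs.** SAP 9.1 tabulates compliance as ">120%, >100-<=120%, >=75-<=100%, <75" percent. It also lists "Basic summaries of number of days a participant missed IP intake". Protocol 10.4.4 gives as a possible major deviation "subjects for whom compliance during the double-blind treatment period was not between 75% and 120" percent.

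**Declaring changes.** SAP Section 1 says: "Differences in descriptions or explanations provided in the study protocol and this SAP, are discussed in Section 13". Section 13 covers the ITT, PD and PK analysis sets and CSP sections 2.3, 5.11 and 10.4.2. It has no entry for CSP 10.4.5 or for compliance.

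**The concern.** A compliance ratio is informative only if an untaken dose stays in the denominator. Once missed doses are dropped from it, numerator and denominator shrink together, and the result says little about adherence. The better the missed doses are recorded, the closer every participant moves to 100%.

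Three consequences follow:

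- The below-75% row in SAP 9.1 would be empty or understated.
- The 75% to 120% deviation criterion in protocol 10.4.4 would miss under-dosing if it is computed from this variable. Neither document says which formula that criterion uses.
- A study report could show near-complete compliance next to a table of many missed days.

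Two further problems sit in the same section. The rule for missing return counts is a worst case only if untaken tablets lower compliance, which the denominator rule prevents when missed doses come from pill counts. The treatment-duration formula refers to itself and cannot be programmed as written.

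**Working it through.** The documents give no compliance figure to reproduce, so this is direct arithmetic on the stated rules.

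**Inputs**

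- Scheduled doses for a completer: once daily for 52 weeks (protocol 1.6), D = 52 × 7 = 364.
- Missed doses m, or true adherence a = (D − m)/D: illustrative values.
- Share c of missed doses captured in the diary: assumed, because neither document gives a capture rate. SAP 6.4.2 says participants cannot enter missed doses retrospectively, so incomplete capture is possible.
- The pill count is taken to equal the doses actually taken.

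**Step 1. All missed doses captured, or derived from pill counts**

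- Protocol 10.4.5, plain reading: (D − m)/D.
- SAP 6.4.7: (D − m)/(D − m) = 100% for any m below 364.
- With m = 182: protocol 182/364 = 50.0%; SAP 182/182 = 100%.
- With m = 92: protocol 272/364 = 74.7%, in the below-75% row; SAP 272/272 = 100%.

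**Step 2. Partial diary capture**

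SAP compliance = a / (1 − c(1 − a)). For example, a = 0.50 and c = 0.8 gives 0.50/(1 − 0.8 × 0.50) = 0.50/0.60 = 83.3%.

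Setting this below 0.75 and solving for a gives a < 0.75(1 − c)/(1 − 0.75c). For c = 0.8: 0.75 × 0.2/(1 − 0.6) = 0.15/0.40 = 37.5%.

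| Captured share c | SAP value, a = 50% | SAP value, a = 74% | True adherence needed to reach the below-75% row |
|---|---|---|---|
| 0 | 50.0% | 74.0% | below 75.0% |
| 0.5 | 66.7% | 85.1% | below 60.0% |
| 0.8 | 83.3% | 93.4% | below 37.5% |
| 0.95 | 95.2% | 98.3% | below 13.0% |
| 1 | 100% | 100% | never |

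For the participant with m = 182, the below-75% row is reached only if c is under about 0.67. For m = 92, c must be under about 0.014.

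**Step 3. Missing return count in a fully adherent participant**

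Assume one kit covers the 84 days from Week 16 to Week 28; the documents give no kit size. The rule sets doses taken from that kit to zero, so the numerator is 364 − 84 = 280.

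- Missed doses from the diary (none recorded): 280/364 = 76.9%.
- Missed doses from pill counts (84): 280/(364 − 84) = 280/280 = 100%.

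Two programmers could follow the same text and obtain different values.

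**Step 4. Is it declared?** The Section 13 entries, read against protocol 10.4.5, show no compliance row, although that section lists a change as small as tabulating medical history rather than only listing it.

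**The case against.** The strongest reply is that little is lost from the report. SAP 9.1 separately tabulates participants with at least one missed intake and the number of days missed. It also shows exposure duration and treatment duration, whose gap is evidently meant to reflect missed dosing. No hypothesis test, estimand or analysis set uses compliance, and site action under protocol 5.5 rests on drug accountability. All of this stands, and it limits the finding to reporting. It does not rescue the compliance table itself.

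Second, the below-75% row need not be empty. The SAP names the diary and eCRF first and uses pill counts for missed doses only when these are unknown, so a poorly kept diary still yields low values. At zero or 25% capture, the participant taking half the tablets scores 50.0% or 57.1% (0.50/(1 − 0.25 × 0.50)). That is right, and the supportable claim is an upward bias of unknown size that reaches 100% at full capture. But the ratio then depends on how badly the diary was kept, and participants just under 75% are lost at almost any capture rate.

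Third, protocol 10.4.5 does not define expected doses, so the departure is inferred from its plain reading. This is fair, but protocol 5.5 exempts only Investigator-instructed safety interruptions, which leaves ordinary missed doses counting against the participant.

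Fourth, the deviation consequence is conditional: protocol 10.4.4 only says that deviations may include noncompliance, and SAP 7.2 does not refer to 6.4.7. That also stands.

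Fifth, the conflict over missing returns could be read as an ambiguity about which source takes precedence, and the treatment-duration line as a slip whose intended term is plain from the exposure formula above it. Both readings are reasonable, and both still need a correction.

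**Conclusion.** The concern holds. As written, the SAP rule gives 100% compliance for any level of adherence above zero when missed doses are fully captured or taken from pill counts, and an inflated value when they are partly captured. The example of 182 of 364 tablets moves from 50% to 100% at full capture, or to 66.7%, 83.3% or 95.2% at assumed capture of 50%, 80% or 95%. The size in this trial is unknown because the capture rate is not stated.

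The departure from protocol 10.4.5 rests on the plain meaning of expected doses together with protocol 5.5, and it is not declared in Section 13. The effect is limited to the SAP 9.1 compliance categories and, conditionally, the 10.4.4 deviation listing. Efficacy conclusions are not affected. It should be fixed because following the stated rule misreports a planned table; this is more than a missing detail.

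**What to change.** In SAP 6.4.7:

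- Define expected doses as all scheduled once-daily doses from first dose to last dose or permanent discontinuation, with missed doses kept in.
- State whether interruptions instructed by the Investigator for safety are removed, given the exemption in protocol 5.5.
- Use the protocol 10.4.5 counting window (to the day before the visit), or list the difference in Section 13.
- State which source decides the number of missed doses when diary and pill count disagree, and how the missing-return rule enters both parts of the ratio.
- State that the 75% to 120% deviation criterion uses this derivation.
- Correct treatment duration to exposure duration minus days of missed IP.

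The cost is a few sentences, one derivation change and possibly one Section 13 row. The downside is that reported compliance will be lower and more participants may be listed as deviations.

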## 6.4.8. Definition of Prior, Concomitant and Post-Treatment Medications and Procedures

Prior, concomitant, and post-treatment medications (procedures) will be coded using the WHO Drug Dictionary. Procedures will be coded using the Medical Dictionary for Regulatory Activities (MedDRA).

Prior medications (or procedures) are defined as medications (or procedures) that started prior to the first administration of randomized IP. Concomitant medications (or procedures) are defined as medications (or procedures) taken between first administration of randomized IP and last randomized IP plus 28 days. Post-treatment medications are defined as medications taken during the post treatment period where post treatment period starts after last randomized IP plus 28 days. A medication that starts prior to the first administration of randomized IP but continues after the first administration and ends on or before last randomized IP plus 28 days is classified as both prior and concomitant medication. If the end

CONFIDENTIAL Page 35 of 139

date of a medication is partially missing (or fully missing / unknown), and the possible interval for the end date includes the date of the first administration of randomized IP, the medication will be considered concomitant.

A medication (or procedure) that starts after the last dose of randomized IP plus 28 days is not considered concomitant but post-treatment. A medication (or procedure) that starts before last dose of randomized IP but continues after last dose of randomized IP plus 28 days is considered as concomitant and post-treatment.

### 6.4.9. Data Re-allocation for Early Discontinued Participants

Data collected at multiple visits (spirometry, smoking status, vital signs, and laboratory data) recorded at the EOT visit (Week 52, Visit 11) for early discontinued participants will be reallocated. Re-allocation will depend on the actual date of the EOT visit and the closest expected (scheduled) visit date.

For example, if the last visit performed before the EOT visit is Visit 4, the data recorded at the EOT visit will be re-allocated to Visit 5 or 6 depending on the date of the study termination visit. If the study termination visit was performed less than 7 days after the preceding visit, e.g., if the EOT visit was performed in the same visit window as defined in Section 6.5, data other than PEs/AEs/SAEs/AESIs recorded at the EOT visit will not be re-allocated and they will be excluded from the statistical analysis, summary tables and figures. For each assessment, only the visits at which the assessment was scheduled per CSP will be considered for re-allocation. This means that vital signs and laboratory data can be re-allocated to Visits 3, 5, 7 and 9 only. Visit windowing as defined in Section 6.5 will be considered for allocation of data.

Assessments completed every 2nd week, e.g., PGI-S, PGI-C, and QoL-B, will not be reallocated.

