#### 4.2.2.1. Reasons for Withdrawal/Early Discontinuation

A subject may decide to withdraw from the study at any time, for any reason, without prejudice to subsequent care or treatment by the Investigator. When this occurs, the subject should complete all the procedures for the Week 52 (EOT) Visit. Subjects who discontinue the treatment due to AEs should remain under observation until the resolution or stabilization of the AEs. A subject may be discontinued from the study drug treatment before completion for any of the following reasons:

- 1. Subject death
- 2. Subject experiences an AE(s)/SAE(s) that warrants discontinuation, as judged by the Investigator and/or Insmed Medical Director
- 3. A major protocol deviation, which, in the opinion/discretion of the Investigator and/or Insmed, compromises the data integrity of the study
- 4. Subject is noncompliant with the study drug treatment (defined as <80% compliance after at least 2 reeducation efforts)
- 5. Withdrawal by subject
- 6. Termination of the study by the Sponsor
- 7. Investigator discretion
- 8. Subject lost to follow-up
- 9. Subject pregnancy
- 10. Periodontal criteria met (see Section 9.10.3.2)
- 11. Skin criteria met (see Section 9.10.3.1)
- 12. Diagnosis of a malignancy during study, excluding carcinoma in situ of the cervix, or squamous or basal cell carcinoma of the skin
- 13. Serious infection, defined as any infection other than associated with a pulmonary exacerbation that:
  - a. Requires parenteral treatment with an antibiotic requiring admission to the hospital, or parenteral treatment with an antifungal, antiviral, antiparasitic, or antiprotozoal agent
  - b. Is opportunistic, such as TB or other infections whose nature or course may suggest an immunocompromised status
- 14. Subjects who develop neutropenia defined as ANC <1000/mm^3
- 15. Subjects who have the following:
  - a. ALT and/or AST values >3 × ULN and total bilirubin >2 × ULN, excluding confirmed Gilbert's Syndrome
  - b. Confirmed AST and/or ALT >5 × ULN (for more than 2 weeks).

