### 9.7. Clinical Laboratory Evaluations

Numeric laboratory parameters (hematology, chemistry, and urinalysis) will be summarized using descriptive statistics at baseline and at each post-baseline timepoint. Changes from baseline will also be summarized. Descriptive statistics at baseline and change from baseline is limited to continuous data. Categorical data, e.g., urinalysis, will be tabulated as well. A separate by-participant listing will be provided for abnormal values reported.

Shift tables from baseline to the worst result post-baseline including unscheduled assessments will be provided to assess changes in laboratory values. Worst values are results which have the highest distance to the normal range. Reference ranges established by the central laboratory will be used to determine shifts.

Participants experiencing ALT or AST  $\geq$  3 × upper limit of normal (ULN) and total bilirubin > 2 × ULN or ALT or AST  $\geq$  5 × ULN at any point during the study irrespective of an increase in ALP will be tabulated by treatment group. The elevations do not have to occur at the same time or within a specified time frame. Potential cases will be summarized descriptively and listed. In addition, individual (worst) ratio of ULN post-baseline will be presented graphically.

Arithmetic mean plots of laboratory values over time will be prepared for continues laboratory test. The standard deviation will be included at each sampled time point.

A summary of counts of participants with at least one abnormal laboratory value at any visit including unscheduled will also be provided.

Testing for HBcAb, HBsAb, HBsAg, HIV, and HCV will be conducted at Screening only. Those test results will be summarized and listed.

The number and percentage of participants with potentially clinically significant abnormalities (PCSA) will be summarized as defined in Table 10. For the determination of PCSA unscheduled assessment will be considered.

CONFIDENTIAL Page 78 of 139

Table 10: Criteria for Potentially Clinically Significant Abnormalities (PCSA)\*

Parameter		
code	Parameter	PCSA
Clinical Che	mistry	
SODIUM	Sodium (mmol/L)	<120.0 mmol/L
		>155.0 mmol/L
K	Potassium (mmol/L)	<3.0 mmol/L
		>6.0 mmol/L
MG	Magnesium (mmol/L)	<0.4 mmol/L
		>1.23 mmol/L
CA	Calcium (mmol/L)	<1.75 mmol/L
		>3.1 mmol/L
GLUC	Glucose (mmol/L)	<2.2 mmol/L
AST	Aspartate	> (5.0 x ULN) if baseline was normal or $>$ (5.0 x
	Aminotransferase (U/L)	baseline) if baseline was abnormal

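### SAP 6.4.9 leaves some early-discontinuation values out of every table, which conflicts with the worst-value laboratory tables in SAP 9.7, and its trigger is inconsistent

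*SAP*

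**What the plan says.** Protocol 4.2.2.1 states that, when a subject withdraws, "the subject should complete all the procedures for the Week 52 (EOT) Visit". Table 5 of the protocol (footnote a) gives the same visit to those who stop study treatment early. It includes laboratory tests, vital signs, spirometry and an ECG.

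SAP 6.4.9 then deals with "Data collected at multiple visits (spirometry, smoking status, vital signs, and laboratory data) recorded at the EOT visit" for early discontinued participants. These data are moved to the nearest scheduled visit at which the assessment was due: "This means that vital signs and laboratory data can be re-allocated to Visits 3, 5, 7 and 9 only". There is an exception, which applies if the termination visit was "less than 7 days after the preceding visit, e.g., if the EOT visit was performed in the same visit window as defined in Section 6.5". For such a visit the SAP lays down that "data other than PEs/AEs/SAEs/AESIs recorded at the EOT visit will not be re-allocated and they will be excluded from the statistical analysis, summary tables". The exclusion extends to figures.

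SAP 9.7 describes the laboratory tables in different terms. "Shift tables from baseline to the worst result post-baseline including unscheduled assessments will be provided". It also plans counts of participants with an abnormal value at any visit, unscheduled ones included; potentially clinically significant abnormalities (PCSA), again with unscheduled samples; and an ALT/AST and bilirubin table that counts elevations at any time in the study, whether or not they coincide.

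**The concern.** A rule for assigning one value to one nominal visit is written as an exclusion from all analyses, tables and figures. Worst-value and threshold tables do not need one value per visit; they need every post-baseline value. The participants concerned have stopped early, and the reasons for stopping in Protocol 4.2.2.1 include neutrophil and liver-enzyme criteria. If a value that matters is left out, its absence may therefore be related to the abnormality being tabulated.

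The trigger can also be programmed in more than one way, so two programmers following the same text could produce different safety tables.

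**Working it through.** No trial figure needs reproducing. The check sets the sections side by side and counts days from Table 4.

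**1. Does any section restore the excluded values?**

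- SAP 6.1 bars unscheduled data from summaries, except to derive baseline. SAP 9.7 expressly brings unscheduled samples back for shift, abnormal-value and PCSA tables.
- EOT is a scheduled visit (Visit 11), so the wording on unscheduled samples does not clearly restore it. An unscheduled sample could count while an EOT sample taken the same day does not.
- The liver table's coverage of any time in the study contradicts 6.4.9 directly. No order of precedence is given.
- SAP 6.4.4 keeps all assessments in listings.

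**2. How wide is the trigger?** Interval width = last day − first day + 1.

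| Table 4 interval | Days | Width |
|---|---|---|
| Week 4 | 2 to 49 | 48 |
| Week 16 (same width for Weeks 10 to 46) | 92 to 133 | 42 |
| Week 52 | 344 to 378 | 35 |

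Longest gap that still triggers the exclusion, taking Week 16 (target Day 112):

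- Less than 7 days: 6 days.
- Same Table 4 interval, visit on target: 133 − 112 = 21 days.
- Same Table 4 interval, visit 7 days early (Day 105, allowed by the protocol): 133 − 105 = 28 days.
- Same ±7-day window, which Section 6.5 also mentions: Day 105 to Day 119, so 14 days.

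Neither window reading agrees with the 7-day rule. Near Day 1 the mismatch reverses. An EOT visit on Day 6 is 5 days after Day 1, so the day count excludes it, but Table 4 puts Day 1 in an interval of its own.

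**3. Share of calendar days in the exclusion zone.** Denominator: Days 2 to 343, 343 − 2 + 1 = 342. Assumption: all earlier visits fall on target.

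| Reading | Days | Share |
|---|---|---|
| Less than 7 days after clinic Visits 3, 5, 7, 9 | 4 × 6 = 24 | 7% |
| Less than 7 days after any visit, with Day 1 and phone | 9 × 6 = 54 | 16% |
| Same Table 4 interval, after clinic visits | 4 × 21 = 84 | 25% |
| Same Table 4 interval, after any Week 4 to 46 visit | 8 × 21 = 168 | 49% |

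These are shares of days, not of participants. The documents give no distribution of discontinuation times.

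**4. Which visit is the preceding one?** The example in 6.4.9 takes Visit 4, a phone visit at which Protocol Table 5 schedules no laboratory tests or vital signs. With Visit 4 on Day 70 and EOT on Day 75, the gap is 5 days and the EOT sample is excluded. The last scheduled clinic sample was at Visit 3 (Day 28), 75 − 28 = 47 days earlier.

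**5. What would be lost from the tables?** Only a value that changes a participant's classification. For example, ALT of at least 3 × ULN at a scheduled visit followed by bilirubin above 2 × ULN at an excluded EOT visit would meet the 9.7 liver criterion only if the EOT value counts.

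**6. Other assessments.** SAP 9.9 plans only by-visit summaries of vital signs, so the exposed use is the blood-pressure threshold check in 9.4. ECG is not in the opening list of 6.4.9, but the exclusion is worded for everything except the named event types. Whether it reaches the maximum post-baseline QTcF table in 9.10 is unclear.

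**The case against.** The strongest reply is that 6.4.9 is headed as a re-allocation rule, and 9.7 sets its own rule for worst-value tables. Since 9.7 evidently overrides the general bar on unscheduled data in 6.1, it could equally override 6.4.9. That is a fair reading, and it makes this an unresolved conflict, not a settled loss. It does not remove the conflict: 9.7 names unscheduled samples and is silent on excluded EOT values, while 6.4.9 names tables and figures without exception.

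A reader might infer that the values are deleted. They are not: listings keep them, abnormal values and potential liver cases are listed separately, and AEs, SAEs and AESIs from that visit remain.

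A reader might also infer that the tables will under-count the very abnormalities that led to stopping. The documents do not support that. A participant whose earlier sample already showed neutrophils below 1000/mm³ is in the PCSA count, because its threshold (below 1.0 × 10⁹/L) is the same. The protocol's isolated ALT/AST criterion requires a confirmed elevation lasting more than 2 weeks, which does not fit a first abnormal sample followed by EOT within 6 days. Participants who stop treatment are encouraged to attend later visits, so later samples may exist.

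The ±7-day reading of the window is legitimate and narrows the gap, but it still allows 14 days against 6.

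**Conclusion.** The point holds as a conflict between SAP 6.4.9 and 9.7, together with an inconsistent trigger. On a literal reading of 6.4.9, a classification-changing EOT value is left out of the shift, abnormal-value, PCSA and liver tables.

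The number of participants affected cannot be derived: the documents state neither the early-stopping rate nor how close EOT visits fall to earlier ones. Multiplying assumed percentages would count EOT visits, of which missed abnormalities are only a subset. What can be stated is the range of the trigger, from 6 days to 28 days after the preceding visit for a Week 16 visit held within the protocol window, and that the preceding visit may have no sample. The calendar-day shares rest on earlier visits falling on target.

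The matter should be settled because it concerns safety tables in a group that may have stopped for safety, and the repair is cheap.

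**What to change.** In SAP 6.4.9:

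- Limit the exclusion to by-visit summaries and repeated-measures models. Section 6.5 already selects one observation per interval.
- State that all post-baseline EOT values, whatever their timing, enter the 9.7 worst-value, abnormal-value, PCSA and liver tables, the 9.4 blood-pressure threshold check and the 9.10 maximum post-baseline QTcF table.
- Use one trigger, counted in days from the last visit at which that assessment was actually taken, and delete the same-window example.

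A cross-reference in 9.7 would settle precedence. The cost is SAP wording and a flag in the analysis datasets; no new data are needed.
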